Objective 1: To refine the SPARK platform to promote self-report symptom screening.

Specific Eligibility: All participants meeting overall eligibility criteria.

Procedure: After collection of demographic data, we will ask children to evaluate SPARK. In-person, individual interviews will be conducted with a semi-structured format using the TAL technique of cognitive interviewing. Participants will be purposively sampled in groups of five to maximize variation by age, diagnosis, inpatient status and treatment status active/completed. This aim will occur on a laptop.

We will ask the participant to explore the SPARK landing page (Figure 2) which contains 3 icons representing children receiving cancer treatment, family members and

healthcare providers. Next, we will ask the participant to click the child icon which will take him/her to the patient main page (Figure 2). The patient main page includes 3 icons which direct the user to: (1) Do SSPedi now; (2) See reports; and (3) View description of the benefits of using SSPedi. Finally, from “See reports”, the participant will be asked to view and describe four hypothetical SSPedi reports. Two reports will illustrate single SSPedi administrations: one represents highly bothersome symptoms and one represents symptoms that are not bothersome. Two reports will illustrate trends over time: one showing improving and one showing worsening of symptoms.

To evaluate understandability, with each page, the participant will be asked what each icon or element means and will be encouraged to click on icons to progress through SPARK. Participants will be asked to verbalize their thought process as they navigate through SPARK and will be continuously prompted to TAL. The interviewer will be a trained clinical research associate or research nurse with expertise in qualitative approaches and cognitive interviewing. We have previous experience both with the TAL approach and with iterative instrument development in this patient population.^{13, 11} A second research associate will observe the interview and rate understandability of each SPARK element and the symptom reports on a 4-point Likert scale ranging from 1=“completely incorrect” to 4=“completely correct”.

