Interview results will be summarized and reviewed after every 5 interviews by research

team members to determine whether our approach or the script requires modification. Minor edits to SPARK may be made. After 15 and 30 participants have been enrolled, the same Review Panel from aim 1 will meet to evaluate the comments and decide whether to modify SPARK. If compliance is low after 15 participants, we may provide the iPad in person daily for inpatients (similar to outpatients) for the next 15 participants.

Analysis and Sample Size: We will describe the proportion of children who complete screening on at least 60% of on-study days, or 3 of 5 days. Based upon our experience with SSPedi, we anticipate that at least 75% of participants should be able to achieve this level of compliance.

We will describe the proportion of participants who state that SPARK is easy or very easy to use, who rate usefulness as 4 or 5 (5="extremely useful") and who correctly interpret SSPedi reports. Analysis of qualitative comments will be descriptive.

We will include 30 participants. Assuming that 75% of participants achieve SSPedi completion on at least 60% of days, this sample size provides a two-sided 95% confidence interval with limits of 56-89%; this precision will be adequate for our purposes.

Objective 3: To determine the feasibility of an RCT of symptom feedback to healthcare providers versus standard of care.

Specific Eligibility: Same as aim 2.

Procedures: In this pilot multi-center RCT, we will randomize children to either undergo daily symptom screening for 5 days with symptom reports provided to the healthcare team or standard of care. The primary endpoint, feasibility, will be met if at least 30 participants are enrolled within one year and if at least 75% complete symptom screening on at least 60% of on-study days. Participants will be randomly allocated 1:1 to the intervention group or to the control group. The randomization sequence will be computer generated and stratified by HSCT versus non-HSCT and institution. Block sizes will not be disclosed and the allocation sequence will be concealed.

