For those randomized to the intervention arm, symptom screening using SPARK will be completed once daily for 5 days on an iPad using the approach refined in aim 2. Daily SSPedi reports will be printed and provided in the patient chart. On days 1 and 3±1, a report describing symptoms that are "a lot" or "extremely" bothersome will be emailed to the physician providing direct medical care..

For those randomized to the control arm, a clinical research associate will visit the participant on days 1 and 5±1 and will obtain SSPedi scores on an iPad. Reports will not be printed or emailed to the physician.

For both arms, participants will be interviewed on day 5±1 using a semi-structured

format. We will identify aspects of the study which they liked and which they didn't like and potential barriers and facilitators to participation in a future RCT. Secondary endpoints will also be collected. For the intervention arm, questions regarding general impressions and ratings of ease of use and usefulness will be the same as in aim 1.

The primary outcome feasibility will be met if at least 30 participants are enrolled within one year and at least 75% complete at least 60% of evaluations.

Secondary endpoints include potential efficacy outcomes for the definitive RCT; they will be obtained on day 5±1. We will include SSPedi total scores and individual symptom scores. We will also include a pain scale (Faces Pain Scale Revised) and the PedsQL 3.0 Acute Cancer Module. This measure is a multidimensional instrument that is reliable and valid in children with cancer.¹³⁻¹⁷ It assesses pain and hurt, nausea, procedural anxiety, treatment anxiety, worry, cognitive problems, perceived physical appearance and communication. The self-report 7 day recall version will be used. We will also measure documentation of symptoms and intervention provision for symptom control as abstracted from the health record.

Analysis and Sample Size: Feasibility will be defined as ability to enroll 30 participants within one year and compliance with SSPedi evaluations as defined above. For the SSPedi, pain and QoL scores, we will calculate variance to facilitate sample size calculations for the future definitive trial. Description of symptoms and intervention provision will be descriptive. In the event of missing data, multiple imputation approaches will be used.

JUSTIFICATION FOR METHODOLOGICAL CHOICES

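### Do SSPedi printouts placed in one arm's charts bias the aim 3 measure of symptom documentation?

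*Protocol*

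**What the plan says.** All the relevant text is in the Protocol under Objective 3.

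- **Intervention arm (Procedures).** Children screen once daily for 5 days, and "Daily SSPedi reports will be printed and provided in the patient chart". On days 1 and 3±1 the physician is also emailed a report of the most bothersome symptoms.
- **Control arm (Procedures).** A research associate obtains SSPedi scores on days 1 and 5±1. "Reports will not be printed or emailed to the physician".
- **Endpoint.** The secondary endpoints are introduced as including candidate efficacy outcomes for the definitive trial, obtained on day 5±1. After the SSPedi, pain and quality-of-life measures, the paragraph ends: "We will also measure documentation of symptoms and intervention provision for symptom control as abstracted from the health record".
- **Analysis and Sample Size.** For this measure: "Description of symptoms and intervention provision will be descriptive". For the others: "For the SSPedi, pain and QoL scores, we will calculate variance to facilitate sample size calculations for the future definitive trial".
- **Primary endpoint.** Feasibility: 30 participants enrolled within a year, and "if at least 75% complete symptom screening on at least 60% of on-study days".

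**The concern.** The study adds sheets describing symptoms to the charts of one randomised arm and withholds them from the other. It then measures how well symptoms are documented by reading the health record, of which the chart would ordinarily be part. A printed SSPedi report is, on its face, a record of symptoms. With no restriction on author or source, an abstractor could count it, and the intervention would then be scored as its own outcome.

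A descriptive analysis gives no protection, because the distortion would lie in the measurement and not in a test. What would be at stake is the pilot's picture of one candidate outcome. Symptom documentation could look responsive to feedback when the treating team had written nothing different, and the definitive trial might adopt it for that reason.

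**Working it through.** **1. What the text fixes and what it leaves open.** It fixes that printouts go into the chart in one arm only, and that the endpoint comes from the health record. It leaves open whether study-generated sheets count, whose entries are read, over what period, and whether scoring is per child, per day or per symptom. The problem arises only if the first of these is answered in one particular way.

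**2. Which answer is the natural one.** The endpoint sentence couples documentation with the provision of interventions for symptom control. Provision is an act of the care team, and documentation beside it reads most naturally the same way. The Summary and the section on the importance of the idea both say that symptoms go unaddressed partly because clinicians do not ask about them. The outcome that answers that rationale is what the treating team records.

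**3. The algebra if printouts were counted.** Let *d* be the probability that clinicians document a symptom, the same in both arms, and *s* the probability that a counted printout shows it (intervention arm only).

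- Control rate: *d*.
- Intervention rate, if the two are independent: *d* + (1 − *d*)*s*.
- Spurious difference: (1 − *d*)*s*.
- Without independence, the difference lies between max(0, *s* − *d*) and min(*s*, 1 − *d*).
- If printouts are not counted, *s* = 0 and the difference is 0.

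The direction is therefore clear: any artefact can only favour the intervention.

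**4. Can it be sized?** Only the supply of printouts can be approached.

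- The allocation statement is "Participants will be randomly allocated 1:1 to the intervention group or to the control group". With 30 enrolled, an equal split gives 15 per arm (assumed).
- Suppose the compliance criterion is met within the intervention arm. Then 0.75 × 15 = 11.25, so at least 12 children; 60% of 5 days is 3 days.
- If every completed screen is printed, that is at least 12 × 3 = 36 printouts in the intervention arm, against none in the control arm.

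Printouts would thus be common. Turning that into a difference in documentation needs *d*, the share of printouts that would count, and a scoring unit. The protocol gives none of these. The share need not be 100%, since a report may show little: of the two single-administration sample reports in Objective 1, "one represents highly bothersome symptoms and one represents symptoms that are not bothersome". Any range in percentage points would reflect the values chosen for these inputs and not the protocol, so none is given.

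**5. What depends on the measure.** The protocol attaches no computed figure, test or sample size to it. Variances for planning the definitive trial are to be calculated for the SSPedi, pain and quality-of-life scores, none of which comes from chart abstraction. The feasibility decision uses enrolment and screening compliance. Provision of interventions is not directly inflated, because a printout is not an intervention.

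**The case for a change.** The best argument for a change is that this is more than silence on a detail. The protocol itself creates the overlap by fixing both arm-specific chart content and an unrestricted data source. Aim 3 runs at five sites, which could handle the printouts differently if no rule were given. The measure is listed among outcomes that may serve the definitive trial. One sentence would remove the risk without touching procedures, sample size or the primary endpoint.

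Much of this stands. The overlap exists, its direction is known, and describing the data instead of testing them would not remove it. A line in the abstraction instructions that confines the count to entries by the treating team, and logs printouts separately as a fidelity item, would be good practice.

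It does not show that the protocol is wrong. A hazard that appears only under a counting rule the protocol never states is a gap in detail, and such detail is usually settled in an abstraction form or analysis plan. Using five sites makes a common form desirable; it does not make the less plausible reading more likely. The definitive trial would also have to define this outcome before relying on it.

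**Conclusion.** No change to the plan follows. The artefact is zero on the natural reading, in which symptom documentation means what the treating team records. If study printouts were counted, the descriptive summary would favour the intervention by an amount that cannot be determined from the protocol. That outcome needs two things the protocol does not state: that the sheets placed in the chart belong to the abstracted record, and that abstractors count them.

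The reach is small in either case: one secondary, descriptive measure in a pilot aiming for 30 participants, with no test, planned variance estimate or feasibility criterion depending on it. The conclusion rests on abstractors applying the sensible reading or being told to do so in working documents that are not at hand. No stated rule or figure in the protocol needs correcting.

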children with cancer and HSCT recipients can be enabled to report and track symptoms and for this information to be readily available to clinicians. The expected result is a transformation from our current non-systematic healthcare provider-centered approach to symptom management to a systematic child-centered approach. The ultimate result will be improved symptom control and better QoL for children receiving cancer treatment.

METHODOLOGY

Overall Eligibility: We will include children with cancer and HSCT recipients who are 8-18 years of age at enrollment and who can understand English. Participants may be inpatients or outpatients, and may be actively receiving cancer treatment or may have completed treatment. Exclusion criteria will be illness severity, cognitive disability, or visual impairment that precludes utilization of SPARK according to the healthcare team. Additional criteria apply to aims 2 and 3.

Sites: Aims 1 and 2 will occur at a single site, The Hospital for Sick Children (SickKids) in Toronto. Aim 3 will occur at 5 sites: SickKids and the children's hospitals in Vancouver, London, Hamilton and Ottawa.

Ethics: Research Ethics Board (REB) approval will be obtained at all sites. Informed consent and assent (if applicable) will be obtained from all participants.

SPARK Development: With support from an Infrastructure Grant from the Garron Cancer Centre, we worked with a website developer (Translucent Computing) and a choice architecture expert ([name]) to create a draft version of SPARK (Figure 2).

SPARK development has incorporated several design features. First, efforts have focused on maximizing the use of icons and images rather than text based upon choice architecture expert input. Second, usability has been emphasized. In order to account for the wide age and developmental ability range, we have integrated audio assistance and synonym lists for younger children. Third, SPARK is accessible on multiple platforms such as a personal computer, tablet or smartphone. Fourth, we have developed an on-line, secure database located at SickKids. Data transmission occurs via wireless network systems and all processes are HIPPA/PHIPPA compliant. Fifth, SSPedi reports allow each child to track his/her symptoms over time and will permit healthcare providers to view their patients' SSPedi results. Currently, SPARK has only been evaluated by research team members. The following describes the specific methodology for each aim.

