We will describe the proportion of participants who state that SPARK is easy or very easy to use, who rate usefulness as 4 or 5 (5="extremely useful") and who correctly interpret each SPARK element. Analysis of qualitative comments will be descriptive. Based upon our previous experience with this technique, we anticipate the conduct of between 8-16 iterations with 5 participants per iteration for a total of 40-80 participants.

Objective 2: To determine the proportion of children who complete symptom screening on at least 60% of on-study days and to determine the most effective ways to communicate symptom screening results during a longitudinal study.

Specific Eligibility: Participants meeting overall eligibility criteria and who are expected to be in hospital or in clinic daily for at least 5 days.

Procedure: Participants will complete symptom screening using refined SPARK from aim 1, once daily on a study-supplied iPad, for 5 days. Five days was chosen to allow longitudinal daily evaluation but preserve feasibility as few children are admitted or seen daily for longer than 5 days. For inpatients, daily reminders to complete SSPedi will appear on the iPad, by text or by email depending on preferences and availability. Reports will be available to the child at any time. For outpatients, research associates will provide the iPad in person daily and reports may be viewed at those encounters.

Individual interviews will be conducted on day 5±1 using a semi-structured format similar to that used in aim 1. The interviewer will ask if the participant viewed any of the reports and what was done with the information, including whether the information was shared with healthcare providers. Next, the interviewer will generate that child's last SSPedi report and all reports since study entry. If the child did not complete any SSPedi evaluations, then hypothetical reports will be shown. The participant will be asked to interpret the reports in a similar fashion as aim 1 using TAL. Suggestions for modifications to improve clarity and meaning will be solicited, particularly if the child is incorrect in report interpretation.

Next, we will ask about the participant's experience with daily SSPedi completion. We will ask about potential facilitators and barriers to daily reporting. At the end of the interview, questions regarding general impressions and ratings of ease of use and usefulness will be the same as in aim 1.

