Cohort: A lower age limit of 8 years was chosen as this is the youngest age for which SSPedi has been evaluated. We plan to conduct this study among English-speaking children because SSPedi is currently only available in English. Translation to other languages will be an important future initiative.

Timing: Early psychometric testing of SSPedi has been promising. Even though psychometric evaluation of SSPedi is in progress, it is appropriate to begin evaluation of SPARK. In the unlikely scenario that SSPedi total score is not reliable or valid, individual SSPedi items can still be incorporated into SPARK and only the overall SSPedi scores would be deleted.

Focus on inpatients and clinic patients: There are many contexts in which SPARK may be helpful including inpatient, clinic, home and following completion of therapy. We have chosen to begin this research program with those seen for 5 consecutive days but appreciate that expanding to other contexts is a priority.

FEASIBILITY, TIMELINE AND FUTURE WORK

At SickKids, there are 350 new cancer diagnoses and 100 HSCT procedures performed annually. Thus, we anticipate 150 eligible patients for aim 1 and 50 eligible patients for aims 2 and 3 annually. Assuming 40-60% acceptance rate, each aim will require 1 year for enrollment (aim 3 occurs at 5 sites).

Aims 1 and 2 will require 2.5 years which incorporates time for Review Panel meetings and software development and modifications. Aim 3 will require 1.5 years to allow time for study start-up at the 4 non-SickKids sites. One final year will be required for analysis and manuscript preparation, resulting in a total timeline of 5 years.

In the future, we plan to link the data from the longitudinal studies of SSPedi and SPARK to data in the Cancer in Young People – Canada (CYP-C) program. CYP-C is a national pediatric cancer database which includes all children 0 to < 15 years of age with cancer since 2001. Linking these data sets will allow us to develop predictive models of symptom burden using patient and institutional characteristics and to describe survival outcomes associated with uncontrolled symptoms. Therefore we plan to ask participants in this randomized trial for permission to link trial data with the data in CYP-C.

Expertise, Experience and Resources

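### Does the one-year enrolment estimate for aim 2 need correcting, given the protocol's own accrual figures?

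*Protocol*

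**What the plan says.** The section Feasibility, Timeline and Future Work starts from the annual case load at SickKids and concludes: "we anticipate 150 eligible patients for aim 1 and 50 eligible patients for aims 2 and 3 annually". It continues: "Assuming 40-60% acceptance rate, each aim will require 1 year for enrollment (aim 3 occurs at 5 sites"). The multi-site remark in that sentence applies to aim 3 only.

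The same section builds the calendar: "Aims 1 and 2 will require 2.5 years which incorporates time for Review Panel meetings and software development and modifications". It adds 1.5 years for aim 3 and one year for analysis and writing, "resulting in a total timeline of 5 years".

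The sizes and sites are given elsewhere:

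- Methodology, Sites: "Aims 1 and 2 will occur at a single site, The Hospital for Sick Children (SickKids) in Toronto".
- Objective 1, Analysis and Sample Size: the interviews are expected to run "for a total of 40-80 participants".
- Objective 2, Analysis and Sample Size: "We will include 30 participants".
- Objective 2, Procedure: "Participants will complete symptom screening using refined SPARK from aim 1". Aim 2 enrolment therefore follows aim 1.

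**The concern.** The feasibility section offers a range of acceptance rates and a single enrolment time, as if that time held over the whole range. For aim 2 it does not. There is one site, and the yearly yield reaches 30 only at the top of the range. Because aims 1 and 2 run in sequence, a slower aim 2 uses up the 2.5 years that must also hold the Review Panel meetings and software work, and any overrun carries into the five-year total.

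A related worry concerns aim 3. By the same figures SickKids alone might enrol 20-30 children, and the enrolment criterion for the five-site pilot is at least 30 in a year. The criterion could then be met with little contribution from the other four hospitals.

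At stake would be the realism of the schedule and, for aim 3, how much a pass says about accrual outside the lead site.

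**Working it through.** **Inputs.** Eligible children per year at SickKids: 150 for aim 1, and 50 for aims 2 and 3. Acceptance: 40-60% (Feasibility, Timeline and Future Work). Sizes: 40-80 for aim 1 and 30 for aim 2 (Analysis and Sample Size under Objectives 1 and 2).

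**Formula.** Enrolment years = children needed / (eligible per year x acceptance).

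**Aim 2 against the stated one year.**

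- 40%: 50 x 0.40 = 20 a year; 30/20 = 1.5 years
- 50%: 50 x 0.50 = 25 a year; 30/25 = 1.2 years
- 60%: 50 x 0.60 = 30 a year; 30/30 = 1.0 year

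The stated year is reproduced at 60% only.

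**Another reading.** The range may be the span of rates the aims require for one year each. Aim 1 at the midpoint of its size needs 60/150 = 40%, and aim 2 needs 30/50 = 60%. This reproduces one year for both, but the text does not assign rates to aims, and aim 2 still needs 60%.

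**Aims 1 and 2 in sequence, enrolment only (years).** Aim 1 yields 60, 75 or 90 children a year at 40%, 50% or 60%.

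| Acceptance | Aim 1 = 40 | Aim 1 = 60 | Aim 1 = 80 |
|---|---|---|---|
| 40% | 0.67 + 1.50 = 2.17 | 1.00 + 1.50 = 2.50 | 1.33 + 1.50 = 2.83 |
| 50% | 0.53 + 1.20 = 1.73 | 0.80 + 1.20 = 2.00 | 1.07 + 1.20 = 2.27 |
| 60% | 0.44 + 1.00 = 1.44 | 0.67 + 1.00 = 1.67 | 0.89 + 1.00 = 1.89 |

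Enrolment alone exceeds 2.5 years in one of the nine cells and equals it in one.

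**Time for panel and software work.** The protocol gives no figure. Subtracting two stated one-year enrolments from 2.5 leaves 0.5 year, which is an inference. Adding it to each cell gives 2.67, 3.00 and 3.33 years at 40%; 2.23, 2.50 and 2.77 at 50%; 1.94, 2.17 and 2.39 at 60%. Five of the nine cells stay within 2.5 years. The central cell (50%, 60 children) gives 2.00 + 0.50 = 2.50, which is the stated figure.

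**Five-year total.** The stated sum is 2.5 + 1.5 + 1.0 = 5.0. At 40% with the inferred 0.5 year it becomes 5.17, 5.50 or 5.83 years for aim 1 sizes of 40, 60 or 80. The largest overrun is 0.83 year.

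**Aim 3.** SickKids at 40-60% gives 20-30 a year. The target is a minimum, so 20/30 to 30/30 is not that hospital's share of enrolment. A share needs the total, and the protocol gives no volumes for the other four sites.

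**The case for a change.** The case for a change is that the feasibility section is contradicted by its own inputs. The one-year figure for aim 2 fails over all of the acceptance range except its upper end. At 40%, if aim 1 takes its stated year, enrolment uses 1.0 + 1.5 = 2.5 years and leaves nothing for the panel and software work that the 2.5 years is said to include. A correction would cost a few sentences. For aim 3, reporting enrolment and acceptance by site would show whether the other hospitals contributed.

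The aim 2 arithmetic stands. The wider claim, that 2.5 years cannot hold at 40%, goes too far. With 40 children in aim 1, enrolment takes 2.17 years and about four months remain. Saying that 40% never fits depends on the inferred 0.5 year, which is itself derived from the disputed one-year figures. The Review Panel also meets during accrual (after every 10-20 participants in aim 1, and after 15 and 30 are enrolled in aim 2), and the protocol does not say that enrolment pauses for it.

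The aim 3 argument identifies no error. The criterion is a valid target for total enrolment. Nothing in the protocol says that a pass demonstrates accrual at every site. Randomization is stratified by institution, so counts by site will be known, and analysts would ordinarily report them.

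**Conclusion.** No change is needed. By the protocol's own figures aim 2 needs 1.0 to 1.5 years of enrolment, and the stated year is its most favourable case. That is an optimistic rounding in a planning paragraph. Aim 2 is descriptive, enrols a fixed 30 children and has no deadline that counts towards success. The planned 95% interval of 56-89% depends on the 30 children and the assumed 75%, not on how long they take to enrol. Restating the duration would alter nothing that the trial does or concludes.

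The 2.5-year and 5-year totals are reasonable as central projections: they agree with 50% acceptance, 60 children in aim 1 and 0.5 year for other work. They become tight at 40%, where no time is left for panel and software work unless aim 1 closes with fewer than 60 children. The consequence would be a delay, at most 0.83 year on the five-year total under the inferred 0.5-year allowance. That is a matter of staffing and funding.

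These results assume that aims 1 and 2 enrol strictly in sequence, that the yearly numbers of eligible children are as projected, and that one acceptance rate applies to both aims. The aim 3 enrolment criterion is unaffected.
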